### **List of Abbreviations**

n-3 PUFA: n-3 Polyunsaturated fatty acid  
EPA: eicosapentaenoic acid  
DHA: Docosahexaenoic acid  
g: grams  
IU: international units  
FDA: Food and Drug Administration  
MThBI: Major Thermal Burn Injury  
RCT: Randomized Controlled Trial  
SF-12: short form 12 item questionnaire  
TBSA: total body surface area  
UNC: University of North Carolina  
GFR: glomerular filtration rate  
IDS: investigational drug services  
MAR: medication administration record  
NRS: numeric rating scale  
MCS: mental component score  
PCS: physical component score  
PTSD: post-traumatic stress disorder  
DNA: deoxyribonucleic acid  
RNA: ribonucleic acid  
Cc: cubic centimeters  
PT: physical therapy  
OT: occupational therapy  
RPS: regional pain scale  
DASS: Depression, Anxiety, and Stress Scale  
MOS: medical outcomes survey  
UPLC/ESI/MS/MS: Ultraperformance Liquid Chromatography/Electrospray Ionization Mass Spectrometry  
ELISA: enzyme linked immunosorbent assay  
SAE: serious adverse events  
IRB: institutional review board  
DCC: data coordinating center  
CRF: case report form  
EC: ethics committee

**Study Summary**

Title	Pilot, double-blind, randomized controlled, multi-center study of the effects of fish oil and vitamin D in the prevention of chronic pain following major thermal burn injury.
Short Title	Vitamin D and n-3 PUFAs to prevent chronic pain
IRB Protocol Number	17-1971
Phase	2
Methodology	Double Blind, Randomized Controlled Trial using a 2x2 factorial design
Study Duration	3 years
Study Center(s)	University of North Carolina-Data Coordinating Center University of South Florida Washington Hospital Center
Objectives	Determine the safety and feasibility of administering n-3 PUFAs and Vitamin D to survivors of major thermal burn injury.
Number of Subjects	60
Diagnosis and Main Inclusion Criteria	Major Thermal Burn injury involving less than 30 percent TBSA that are severe enough to require surgery.
Study Product, Dose, Route, Regimen	n-3 PUFA (DHA:EPA 2:3), 2 grams (4 softgels) orally administered once per day for 6 weeks, Vitamin D 2000 IU (1 capsule) once per day for 6 weeks.
Duration of administration	6 weeks
Reference therapy	Matched placebo to fish oil and Vitamin D preparations
Statistical Methodology	Safety will be determined by qualitative and quantitative analysis of the adverse events. Feasibility will be determined by protocol adherence. Estimates of potential efficacy will be determined via repeated measures analysis using mixed effects models.

## 1

## Introduction

This document is a protocol for a human research study. This study is to be conducted according to US and international standards of Good Clinical Practice (FDA Title 21 part 312 and International Conference on Harmonization guidelines), applicable government regulations and Institutional research policies and procedures.

The main objective of this study is to determine whether administration of n-3 polyunsaturated fatty acids and Vitamin D for 6 weeks following Major Thermal Burn Injury (MThBI) is feasible and safe. This phase II, multicenter, randomized controlled trial is a pilot study to determine feasibility, safety and potential efficacy (effect size, sample variation, response to study drug) that can be used to adequately power a larger randomized controlled trial to fully assess efficacy.

### 1.1 *Background*

Nearly 500,000 burn injuries occur annually in the US, and ~40,000 individuals experience major thermal injuries (MThBI) requiring hospitalization. Approximately 3/4 of these individuals require skin grafting, a procedure in which skin is transplanted from a donor site to the site of burn injury (graft site). Up to 60% of MThBI patients receiving skin grafting experience severe ongoing pain despite treatments. New therapeutics that prevent chronic pain, promote recovery, and reduce suffering in MThBI survivors are urgently needed.

Long chain n-3 polyunsaturated fatty acids (PUFAs) represent one of the most promising, untried treatment options to prevent pain in MThBI survivors because they have been demonstrated to be powerful, non-addictive analgesics and also are readily available and easy to administer. A wealth of preclinical and clinical evidence has shown that two of the most well-studied n-3 PUFAs, docosahexaenoic acid (DHA) and eicosapentaenoic acid (EPA), are powerful analgesics, with a potency of effect many times that of oral opioids, and are able to prevent pain. They also have anti-inflammatory, antidepressant, and neuroprotective effects and have been shown to improve general mental and physical health. Oral formulations of DHA and EPA are widely available, and burgeoning evidence from RCTs testing the efficacy of DHA and EPA in other neuro/inflammatory disorders (e.g., rheumatoid arthritis, migraine headache, depression) demonstrate that they are well-tolerated and highly effective.

Vitamin D represents a promising, untried treatment to prevent pain following MThBI because it is associated with worsened chronic widespread pain severity, increased central pain sensitivity, and other chronic pain conditions such as low back pain, and spinal stenosis. Second, available evidence suggests that Vitamin D insufficiency, defined as serum 25-hydroxyvitamin D (25[OH]D) concentrations <74 nmol/L, or less than 20 ng/mL, is a common condition affecting approximately 76% of the U.S. population and disproportionately affects African Americans (97%). Third, in the CNS, vitamin D is known to upregulate two anti-inflammatory cytokines TGF- $\beta$ 1 and IL-4 which have been shown to inhibit chronic pain. Given this data, Vitamin D may be an important modifiable risk factor for chronic pain development following MThBI.

### 1.2 *Investigational Agents:*

DHA and EPA are n-3 Polyunsaturated fatty acids and are active components of fish oil which is known to have anti-hyperlipidemic, anti-inflammatory, and anticoagulation properties. n-3 fatty acids are essential fats that are not synthesized in vivo, and therefore must be consumed through dietary sources. These dietary fats are metabolized into anti-inflammatory, pro-resolving lipid mediators such as resolvins and protectins. DHA is the major component in human tissues, especially neural tissue. EPA is another fatty acid found in human tissues and is known to have anti-inflammatory effects. It is known that DHA does ~ 2 g per day result in a near maximal plasma response. Supplementation of DHA causes a modest increase in EPA levels, but EPA supplementation does not cause an increase in DHA owing to poor enzymatic conversion. Therefore, to increase both DHA and EPA levels in the plasma, the goal of this study, one effective approach is to supplement with both fatty acids.

Vitamin D is a fat soluble nutrient that has been previously associated with chronic pain outcomes. Vitamin D deficiency is common in the population with a US prevalence of 76%. Previous RCTs have used a supplement of 2000 IU of Vitamin D3 targeting an optimal plasma level of 90 nmol/L.

Co-administration of Vitamin D and n-3 PUFA (Fish Oil) has been safety performed in previous RCTs and are potentially synergistic in improving pain outcomes.

### **1.3 Preclinical Data**

Pre-clinical studies have shown that n-3 PUFA and their downstream metabolites are effective anti-inflammatory agents that reduce neuroinflammation (e.g. microglial activation), provide analgesia, and prevent the development of chronic pain following injury. This data supports the use of n-3 PUFA to prevent chronic pain in survivors of MThBI.

### **1.4 Clinical Data to Date**

**Previous studies demonstrate that Vitamin D and O3FA are two safe, and effective treatment options that have been used to treat a range of painful musculoskeletal disorders.** Both Vitamin D and O3FA have been shown to reduce chronic pain severity. Numerous studies, both randomized clinical trials and systematic reviews, have found O3FA to reduce pain related to rheumatoid arthritis, which is an inflammatory pain condition like burn injury. O3FAs have also shown efficacy in randomized controlled trials to treat fibromyalgia, a difficult to manage chronic pain condition. O3FAs have demonstrated improvement in post-operative pain following gastric bypass. O3FAs have shown efficacy in treating osteoarthritis, and there does not seem to be an affect of high or low dose of O3FA. Recent RCT data from a population with coronary artery disease indicates that O3FAs increases physical function, reduced risk of joint replacement and improves pain and stiffness. Clinical evidence from a case series demonstrated that O3FA is effective in reducing neuropathic pain. Strong clinical trial evidence indicates that O3FA is effective to reduce pain and improve quality of life in patients who suffer from migraine headaches migraine headache. Vitamin D has similarly been shown to reduce chronic pain across a range of painful conditions. Clinical trial results demonstrate that Vitamin D supplementation improves symptoms experienced by patients suffering from fibromyalgia, a difficult to treat widespread pain condition. Vitamin D supplementation in a recent clinical trials also improved disability related to low back pain, osteoarthritis and chronic pain related to migraine headache. Not all studies are positive, for example a recent study demonstrated that Vitamin D supplementation did not change analgesic consumption, or improve pain outcomes among the general population; however this study included the general population not those at high risk of chronic pain development as are the individuals we plan to recruit into this study. Taken together, the results of clinical trials assessing the effectiveness of O3FA and Vitamin D to address painful conditions are promising, and given the lack of available treatment options for burn survivors, safety profile of O3FA and Vitamin D, and therapeutic promise we propose O3FA and Vitamin D as a potentially safe and effective preventative treatment option to reduce chronic pain severity and promote opioid cessation following burn injury.

### **1.5 Dose Rationale and Risk/Benefits**

The study will follow a 2x2 factorial design. Two supplements will be used: one will consist of 2 grams of a 3:2 ratio of EPA/DHA consumed orally (4 softgels=4g fish oil) once daily for 6 weeks and another will be 2000 IU daily of Vitamin D (1 capsule). The n-3 PUFA dose has been previously used for studies of other painful conditions and has been associated with a significant increase in the n-3 PUFA level and a reduction in the n-6:n-3 PUFA ratio over a 6 week period. The Vitamin D dose of 2000 IU per day has been previously used in other clinical trials, has been shown to correct Vitamin D to optimal levels, and has been shown to be safe. Participants in the comparator arm for n-3 PUFA will receive 4 grams of soybean/corn oil, which has been safely and effectively used as a comparator in a number of studies.

Chronic pain is associated with reduced mental and physical health and interferes with essential activities of daily life. Currently there are limited treatment options to address chronic pain once it has become established and the overarching aim of this clinical trial is to prevent chronic pain development, therefore there is a critical unmet need of safe, non-addictive, non-invasive preventative treatment options that can

be administered to burn survivors in the aftermath of injury. This study has the potential to benefit participants and future burn survivors and improve pain and general health outcomes. The risks of taking n-3 PUFAs and/or Vitamin D are small. Although n-3 PUFA preparations are well tolerated, potential side effects include fish like taste, belching, indigestion and GI upset, increased bleeding. Acceptance of this limited risk is reasonable based on the anticipated benefits to burn survivors at risk for chronic pain development. Side effects from Vitamin D are rare, however, it is possible that over supplementation of Vitamin D may be associated with headache, loss of appetite, dry mouth, metallic taste, and nausea/vomiting. **The risks to the subjects in experiencing these side effects is balanced against the potential for a new, safe, non-opioid preventative treatment option for chronic pain following MThBI.**

## 2 Study Objectives

**Primary Objective:** To assess the feasibility and safety of administering n-3 PUFAs and/or Vitamin D to MThBI survivors for 6 weeks following MThBI.

**Secondary Objectives:**

[figure not shown]
1. To demonstrate potential efficacy of n-3 PUFAs/Vitamin D on decreasing graft site pain severity in survivors of MThBI requiring surgery. This will provide data on the confidence interval around our model estimates, which will inform a larger clinical trial.
2. Demonstrate the potential efficacy of n-3 PUFAs/Vitamin D on reducing pain interference on important domains of life function measured by the Brief Pain Inventory and SF-12 Mental and Physical Component Scores.
3. To demonstrate the utility of a clinical prediction tool based on a logistic function derived from a previous observational cohort study to enhance enrollment of a population of MThBI survivors at greater risk of chronic pain development.
4. To explore sex as a biological variable to determine whether there are differences in safety and efficacy among women and men.

**Long-Term Aims Beyond the Present Proposal**

To use data collected to design and adequately power a large-scale RCT assessing the efficacy of n-3 PUFAs and/or Vitamin D treatment in decreasing chronic pain in high-risk patients presenting for treatment in the aftermath of MThBI.

## 3 Study Design

### 3.1 General Design

**Study Overview.** Participants will be screened using a logistic risk stratification tool and will be enrolled if their probability of chronic pain is estimated to be  $\geq 0.3$ . Comprehensive phenotyping will be performed on enrolled patients and a plasma sample will be obtained. Randomization will occur and 15 patients will be treated with n-3 PUFAs, Vitamin D, n-3 PUFA+Vitamin D or placebo for 6). Each patient will be assessed at Week 6, Month 3, 6, and 12 following MThBI. Follow-up

telephone assessments will be completed by staff at the UNC Institute for Trauma Recovery. Safety will be assessed with weekly phone calls during the 6 week treatment period.

In this pilot randomized, double-blind study with 2x2 factorial design, eligible patients will be randomized across three sites to receive either n-3 PUFA supplementation, Vitamin D, n-3 PUFA + Vitamin D, or comparator lipid (soybean/corn oil) for 6 weeks following MThBI. Randomization will occur after the enrollment questionnaire within 72 hours of burn injury. Plasma, DNA, and RNA samples will be collected on study enrollment and at 6 weeks following MThBI. Follow-up assessments will be completed at 6 weeks, 3, 6 months and 1 year following MThBI.

### **3.2 Posting on clinicaltrials.gov**

The study protocol will be published to clinicaltrials.gov prior to commencement of the trial. Results will be posted on clinicaltrials.gov when available.

### **3.3 Primary Study Endpoints**

The primary endpoint of this study will examine the safety, feasibility and efficacy of n-3 PUFAs/Vitamin D to improve chronic pain outcomes following major thermal burn injury. **Outcome to assess safety:** Safety outcomes will be met after descriptive review of adverse outcomes, and comparison of adverse events is made across treatment groups by investigative team at the conclusion of the study. **Outcome to assess feasibility:** 60 patients will be enrolled, randomized into one of 4 treatment arms in a 1:1:1:1 ratio, and treated with study drug for 6 weeks following Major Thermal Burn injury severe enough to warrant surgery within a 24 month period. Proportion of participants completing following up at 6 weeks will be reported. The concentration of Vitamin D and n-3 PUFAs will be calculated before and after the 6 week treatment in each treatment arm to assess the response (expect an increase in both Vitamin D and n-3 PUFA in treatment arms). **Outcome to assess efficacy:** Efficacy of Vitamin D/PUFA will be measured by difference in pain severity in treatment arms versus control arms. We will 1) calculate a model estimated mean of chronic pain severity and corresponding 95% Confidence interval in each study group and 2) determine the slope of pain recovery among individuals treated with Vitamin D and n-3 PUFAs relative to control participants using a linear mixed model adjusting for sex, ethnicity, and study site.

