
## **6 Statistical Plan**

### **6.1 Sample Size Determination**

The purpose of this study is to assess study feasibility, safety and to obtain initial effect size estimates and confidence intervals to use in sample size calculations for a larger study. Previous studies of Vitamin D and n-3 PUFAs for the treatment of chronic pain are poorly generalizable to this setting because 1) they examine treatment of established chronic pain states versus developing pain states, 2) do not involve trauma exposure/acute stress, and 3) are not preventive studies. Therefore, this pilot study will be instrumental in demonstrating feasibility and safety of the protocol, and estimates of efficacy along with confidence intervals will be helpful for planning a larger follow-up study.

**Justification for the sample size.** We will target 15 individuals in each group (60 total) so that feasibility and safety may be determined as well as provide potential evidence for efficacy. Below, calculations are provided to justify sample size for each objective.

**Feasibility:** Assuming that observed follow-up will be around 80%, this study will allow us to estimate follow-up rates to within  $\pm 10\%$  with a 95% confidence interval given we reach the enrollment target of 60. Allowing for up to 20% loss, with 30 participants treated in each n-3 PUFA arm of our study, our study is powered at 90% to detect a difference of 2.6% of DHA (an n-3 PUFA) in total fatty acid content considering a standard deviation of 1.3%. This study (30 per Vitamin D arm) is powered at 83% to detect a change of 9 ng/dl in Vitamin D level assuming a SD of 10.5.

**Efficacy:** Allowing for up to 20% loss and assuming a common standard deviation of 2.6 (approximated from our pilot dataset) and no interaction between treatments, randomizing 30 participants to each comparison group (Vitamin D/n-3 PUFA versus control) will allow us to estimate the difference in mean pain severity to within  $\pm 1.4$  using a two-sided 95% confidence interval.

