## 6.2 Statistical Methods

### Primary outcome assessments and analysis:

**Feasibility:** The primary objective of this pilot study is to ensure that we are able to enroll participants and make follow-up assessments. The subsequent study will be considered feasible if we are able to collect follow-up assessments on >80% of enrolled participants at 6 weeks following MThBI, and >80% of participants at 1 year. Medication adherence will be assessed by pill counts at the end of the study and quantitative determination of plasma fatty acid/Vitamin D concentration. The subsequent study will be considered feasible if at least 75% of participants take at least 80% of their assigned medication (per pill count) and there is a statistically significant increase in Vitamin D and fatty acid concentration in treated individuals versus controls. T-tests will be used and a  $p < 0.05$  will be considered statistically significant.

**Safety:** Another main objective of this pilot study is to ensure safety of both treatments as well as combined. To determine safety, we will tabulate the number of serious adverse events in each treatment arm and perform a descriptive review of adverse events in the study, and make a determination about the degree of relatedness of each adverse event with the intervention using CTCAE criteria outlined in Appendix 2. The recorded adverse events in each arm will be tabulated descriptively, but no inferential statistics (p-values and confidence intervals) for comparing arms will be reported.

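### The primary safety outcome counts as met once a review has been done, so no adverse event result could leave it unmet, and no measure of precision is planned for it

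*Combined protocol and SAP*

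**What the plan says.** Section 2 gives the primary objective: "To assess the feasibility and safety of administering n-3 PUFAs and/or Vitamin D to MThBI survivors for 6 weeks following MThBI". Section 3.3 states when the safety part is achieved: "Safety outcomes will be met after descriptive review of adverse outcomes, and comparison of adverse events is made across treatment groups". Section 3.5 adds electronic tracking of adverse events and a qualitative analysis by the investigators.

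Section 6.2 sets out the safety analysis: "we will tabulate the number of serious adverse events in each treatment arm and perform a descriptive review of adverse events in the study", together with a judgement of how far each event is related to the intervention. It adds that "no inferential statistics (p-values and confidence intervals) for comparing arms will be reported".

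On size, Section 6.1 says: "We will target 15 individuals in each group (60 total) so that feasibility and safety may be determined". It then promises: "Below, calculations are provided to justify sample size for each objective". Calculations follow under feasibility and under efficacy. There is none for safety.

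Feasibility, the other half of the objective, is treated differently. It has a stated precision ("Assuming that observed follow-up will be around 80%, this study will allow us to estimate follow-up rates to within" 10 points either way) and criteria that can fail, for example: "The subsequent study will be considered feasible if we are able to collect follow-up assessments on >80% of enrolled participants at 6 weeks".

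**The concern.** An outcome described as met should have some result under which it would not be met. Section 3.3 names only an activity, and no other section supplies a rate, count, margin or decision rule for safety. Followed literally, the text gives the same verdict whatever the adverse event table shows.

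The second part concerns precision. In arms of 15 or fewer, an empty or nearly empty serious adverse event column is weak evidence of safety. The plan says that its size allows safety to be determined but gives the reader no means of seeing how much harm the data would leave open. What is at stake is the report of a primary outcome: it could say that safety was met on data that still allow a substantial event rate.

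**Working it through.** **Inputs.** Planned: 15 per arm, four arms, 60 in total (Section 6.1), so 15 + 15 = 30 receive each agent in the 2x2 design. Actual: Section 6.2 records termination after the 24th patient and gives only that total. Balanced arms of 24/4 = 6, with 12 per agent, are an assumption. The documents give no expected adverse event rate, so the rates of 5% and 10% below are illustrative.

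**The plan's own precision figure.** For follow-up of 80% in 60 patients, the 95% half-width is 1.96 × √(0.8 × 0.2/60) = 0.101, or 10.1 points. This reproduces the stated 10. The plan therefore quantifies precision for the feasibility half of the primary objective. The corresponding step for safety is absent.

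**Upper limit with no events.** The exact (Clopper-Pearson) two-sided 95% upper limit for 0 of n is 1 − 0.025^(1/n).

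| Group | n | Upper limit |
|---|---|---|
| One arm, planned | 15 | 21.8% |
| One agent, planned | 30 | 11.6% |
| All patients, planned | 60 | 6.0% |
| One arm, 24 enrolled, balance assumed | 6 | 45.9% |
| One agent, 24 enrolled, balance assumed | 12 | 26.5% |
| All patients, actual | 24 | 14.2% |

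**Sensitivity to imbalance.** By the same formula, an arm of 4 gives 1 − 0.025^(1/4) = 60.2% and an arm of 8 gives 1 − 0.025^(1/8) = 36.9%. For one agent, 10 exposed gives 30.8% and 14 exposed gives 23.2%.

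**One event instead of none.** For 1 of 15 the exact 95% interval is 0.2% to 31.9%, so the width does not depend on the zero-event case.

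**How often an arm shows no event.** The probability is (1 − p)^n.

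- p = 10%: 0.9^15 = 20.6% for an arm of 15; 0.9^6 = 53.1% for an arm of 6.
- p = 5%: 0.95^15 = 46.3% for an arm of 15; 0.95^6 = 73.5% for an arm of 6.

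**Is there a failing result anywhere?** Sections 3.3, 3.5 and 6.2 give none for safety. Section 6.2 gives several for feasibility: follow-up above 80% at 6 weeks and at 1 year, 75% of participants reaching 80% adherence by pill count, and a significant rise in the measured blood levels.

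**The case against.** The strongest reply is that this is loose drafting in one clause. Section 2 speaks of assessing safety, Section 3.5 of a safety profile, and Section 6.2 of tabulation and review. None of these states a pass rule, and purely descriptive safety reporting without tests is a sound and deliberate choice in a pilot of this size. That stands, and it is why the remedy is rewording rather than a threshold or a test. It does not dispose of the point, because the clause sits in the definition of the primary endpoint and no other section corrects it.

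It can also be said that harm would have consequences regardless. Section 7.5 lets any investigator stop the trial, Section 6.2 plans adverse event reviews after the 20th and 40th patients, the appendix gives grade-by-relatedness guidance for individuals, and Section 7.6 provides for oversight and a medical monitor. A reader might infer from the wording of Section 3.3 that patients were left unprotected. The documents do not support that. These provisions govern conduct, however, and none says when the safety outcome is or is not met.

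Another inference would be that Section 6.2 only counts events. It does not: it also plans a descriptive review and relatedness judgements, and Section 7.6 adds severity grading. What is missing is precision.

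Finally, intervals shown side by side may tempt readers to compare arms. That risk is real but manageable with a table note. The exclusion in Section 6.2 covers intervals for comparing arms and is silent on intervals within an arm.

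**Conclusion.** The concern holds. Section 3.3 makes the primary safety outcome met by completing a review and comparison, and the calculation that Section 6.1 promises for each objective is not given for safety. With no events, the planned size leaves true rates up to 21.8% per arm and 11.6% per agent within the exact 95% interval. For the 24 enrolled, the limits are 45.9% per arm and 26.5% per agent if the groups are balanced.

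Balance should not be read as fact. Only the total of 24 is documented, and blocks stratified on ethnicity and sex (Section 4.3) do not guarantee it at an unplanned stop. Zero events is likewise a reference case and not a reported result.

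A reader might also infer that a verdict of safety met would pass into the larger trial. The documents do not say so. Sections 1 and 2 say that pilot data will inform and power that trial, and the explicit go-ahead criteria in Section 6.2 concern feasibility only. The consequence shown here is confined to how this trial's own safety conclusion is worded and supported. Since enrolment has ended, it affects reporting and not conduct.

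**What to change.** In Section 3.3, change the safety outcome from one that is met after the review to one that is described by it. This brings the endpoint into line with Sections 3.5 and 6.2.

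In Section 6.2, add the number and proportion of participants with at least one serious adverse event and with at least one bleeding event, per arm and per factor margin, each with an exact 95% interval based on actual group sizes. The bleeding assessment is already collected at 3 weeks (Section 5.4) and 6 weeks (Section 5.5). State that the intervals are within-group and that no between-arm inference is drawn.

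In Section 6.1, add a short safety paragraph giving the zero-event upper limits, so that the promise of a calculation for each objective is kept. Require any safety conclusion to quote the relevant upper limit beside it.

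The cost is a few sentences and one table column, with no new data. The safety claim becomes more modest.
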